**Protocol ANB020-003: Amendment 2, 18 MAY 2017**

**Replaces: Amendment 1, 01 DEC 2016**

1. Synopsis

a. Description of Change: Added oral blind placebo-controlled food challenge (BPCFC) on Day 45 (End of Study [EOS] visit).

Purpose for Change: The Day 45 oral BPCFC was added to ascertain duration of ANB020 response in peanut allergy.

b. Description of Change: Updated primary and secondary objectives to specify Day 14.

Purpose for Change: To differentiate primary and secondary objectives from the new exploratory objectives.

c. Description of Change: Added new exploratory objectives.

Purpose for Change: To reflect the changes in the study design (to reflect addition of BPCFC on Day 45).

- d. Description of Change: Updated methodology to include details about BPCFC on Day 45 (EOS visit) and corresponding procedures.  
Purpose for Change: To reflect the changes in the study design.
- e. Description of Change: Added text regarding other EOS visit procedures to perform on Day 45.  
Purpose for Change: To provide clarity for performing other EOS visit procedures on Day 45.
- f. Updated primary and secondary efficacy endpoints to specify Day 14.  
Purpose for Change: To differentiate primary and secondary efficacy endpoints from the new exploratory efficacy endpoints.
- g. Description of Change: Added exploratory efficacy endpoints to assess on Day 45.  
Purpose for Change: To reflect the changes in the study design (to reflect addition of BPCFC on Day 45).
- h. Description of Change: Updated statistical analysis methods for primary and secondary endpoints and added statistical analysis methods for new exploratory endpoints.  
Purpose for Change: To reflect the appropriate statistical analysis methods for endpoints based on the changes in the study design.

2. Section 3.0 (Study Objectives)

- a. Description of Change: Updated primary and secondary objectives to specify Day 14.  
Purpose for Change: To differentiate primary and secondary objectives from the new exploratory objectives.
- b. Description of Change: Added new exploratory objectives.  
Purpose for Change: To reflect the changes in the study design (to reflect addition of BPCFC on Day 45).

3. Section 4.1 (Summary of Study Design)

- a. Description of Change: Updated study design to include details about BPCFC on Day 45 (EOS visit) and corresponding procedures.  
Purpose for Change: To reflect the changes in the study design (to reflect addition of BPCFC on Day 45).
- b. Description of Change: Added text regarding other EOS visit procedures to perform on Day 45.

Purpose for Change: To provide clarity for performing other EOS visit procedures on Day 45.

4. Figure 4.1

- a. Description of Change: Added BPCFC and other assessments on Day 45 (EOS visit) and added additional Day 46 visit to complete the BPCFC if the Investigator decides to split the food challenges into 2 days.

Purpose for Change: To reflect the changes in study design (to reflect addition of BPCFC on Day 45).

- b. Description of Change: Added footnotes regarding details and assessments related to BPCFC as well as other assessments on Day 45 and Day 46.

Purpose for Change: To provide clarity for assessments related to BPCFC as well as other assessments on Day 45 and Day 46.

5. Table 4.1 (Schedule of Events)

- a. Description of Change: Added BPCFC on Day 45 and corresponding procedures with appropriate footnotes.

Purpose for Change: To reflect the changes in study design.

- b. Description of Change: Added Day 46 visit to complete the BPCFC and corresponding procedures if the Investigator decides to split the food challenges into 2 days.

Purpose for Change: To reflect the changes in study design.

- c. Description of Change: Updated footnote 'e' to increase the window period for collecting the blood sample for ex vivo peanut challenge assay.

Purpose for Change: Increased collection window allows flexibility for laboratories to process the blood samples.

- d. Description of Change: Modified footnote 'i' to clarify spirometry or peak flow collection language.

Purpose for Change: To provide clarity for spirometry or peak flow collection time points for patients with a history of asthma.

- e. Description of Change: Added footnotes 'm' and 'n' to provide instructions for BPCFC procedures as well as other procedures on Day 45 and Day 46 visit.

Purpose for Change: To provide guidance regarding study procedures on Day 45 and 46 if the BPCFC is split into 2 days.

- f. Description of Change: Added footnote 'o' to provide instruction for early termination BPCFC and updated early termination (ET) visit header to include reference to footnote 'o'.

Purpose for Change: To provide guidance on when to conduct the BPCFC if a patient terminates from the study before completing all study visits.

6. Section 4.2 (Discussion of Study Design)

- a. Description of Change: Added Day 45 BPCFC in the study design.  
Purpose for Change: To reflect the changes in the study design.

7. Section 4.3.2 (Exclusion Criteria)

Description of Change:

- a. Updated exclusion criteria: Decreased restriction for use of systemic corticosteroids, nonsteroidal, immunosuppressant, or immunomodulating drugs treatments from 8 weeks before screening to 2 weeks before screening.
- b. Updated exclusion criteria: Decreased restriction for use of beta blockers, angiotensin-converting enzyme inhibitors, angiotensin-receptor blockers, or calcium channel blockers from 4 weeks before screening to 2 weeks before screening.
- c. Updated exclusion criteria: Decreased restriction for use of biologics such as omalizumab or any other unconventional allergen immunotherapy from 12 months before screening to 6 months before screening.

Purpose for Change: The timelines for prior use of treatments were determined to be excessive and review of half-lives allow for decreased timeframe.

8. Section 4.3.2 (Exclusion Criteria)

Description of Change: Modified exclusion criteria to allow inclusion of asthma patients requiring Global Initiative for Asthma Assessment (GINA) treatment Step 3.

Purpose for Change: Asthma is commonly found in patients with peanut allergy and affects much of the study population.

9. Section 5.7 (Blinding)

Description of Change: Updated headings in section 5.7 to include unblinding information and provide details for unblinding procedures.

Purpose for Change: To provide unblinding information and instruction should unblinding be necessary during the study.

10. Section 5.8.1 (Excluded Medications)

Description of Change: Updated timelines for excluded medication use to reflect the changes in the exclusion criteria.

- a. Decreased restriction for use of systemic corticosteroids, nonsteroidal, immunosuppressant, or immunomodulating drugs treatments from 8 weeks before screening to 2 weeks before screening.
- b. Decreased restriction for use of beta blockers, angiotensin-converting enzyme inhibitors, angiotensin-receptor blockers, or calcium channel blockers from 4 weeks before screening to 2 weeks before screening.
- c. Decreased restriction for use of biologics such as omalizumab or any other unconventional allergen immunotherapy from 12 months before screening to 6-months before screening.

Purpose for Change: To reflect the changes regarding prior medication use in the exclusion criteria.

## 11. Section 6.0 (Study Procedures)

- a. Description of Change: Added a +1 day visit window for Day 14 visit and clarified the existing study window periods.  
Purpose for Change: To provide scheduling flexibility and to provide clarity for existing study windows.
- b. Description of Change: Added text regarding increased window period for collecting the blood sample for ex vivo peanut challenge assay.  
Purpose for Change: Increased collection window allows flexibility for laboratories to process blood samples.

## 12. Section 6.1.1 (Study Procedures: Oral Blind Placebo-Controlled Food Challenge)

- a. Description of Change: Added text regarding BPCFC to perform on Day 45.  
Purpose for Change: To reflect the changes in the study design.
- b. Description of Change: Modified text regarding administration of BPCFC.  
Purpose for Change: To allow trained study staff to administer OFC.
- c. Description of Change: Added “objective” to assessment of reaction related to the OFC Symptom Scoring Assessment.  
Purpose for Change: To ensure accurate dose is recorded on the OFC Symptom Scoring Assessment Tool.
- d. Description of Change: Deleted text regarding vital signs, physical examination, peak flow or spirometry, and clinical assessment during BPCFC.  
Purpose for Change: Updated text regarding vital signs, physical examination, peak flow or spirometry, and clinical assessment during BPCFC provided under next sub heading (in the following paragraph).

13. Section 6.1.1 (Oral Blind Placebo-Controlled Food Challenge -Criteria for Monitoring and Stopping the Oral Food Challenge)

Description of Change: Clarified language explaining timing of study procedures (vital signs, physical examination, peak flow or spirometry, and clinical assessment using oral food challenge Symptom Scoring Assessment Tool) during BPCFC.

Purpose for Change: To provide clarity regarding timing for assessments (vital signs, physical examination, peak flow or spirometry, and clinical assessment) during BPCFC.

14. Section 6.2.1 (Blood Volume)

Description of Change: Updated blood volume to be collected at Screening and Day 1 (Pre-dose) and added corresponding footnote.

Purpose for Change: To reflect the extended collection window for ex vivo peanut challenge assay either at screening or on Day 1 and footnote provides additional detail on potential blood volumes.

15. Section 6.2.2 (Day 1 Randomization)

Description of Change: Added language to collect the blood sample for ex vivo peanut challenge assay on Day 1 if it was not collected during screening.

Purpose for Change: To provide additional guidance regarding the blood sample collection window for ex vivo peanut challenge assay.

16. Section 6.2.5 (End of Study)

a. Description of Change: Added Day 45/46 BPCFC and corresponding procedures.

Purpose for Change: To reflect addition of BPCFC at Day 45.

b. Description of Change: Added text to specify EOS visit blood samples to be collected on Day 45.

Purpose for Change: To provide clarity for collecting EOS visit blood samples if visit requires two days.

17. Section 6.2.6 (Early Termination)

Description of Change: Added instructions to perform BPCFC at the ET visit.

Purpose for Change: To provide guidance on when to conduct the BPCFC if a patient terminates from the study before completing all study visits.

18. Section 7.1.1.1 (Reporting of Adverse Events)

Description of Change: Removed repetitive language.

Purpose for Change: To provide clarity on AE reporting procedures.

19. Section 7.1.3 (Vital Signs, Physical Findings, and Other Safety Assessments)

Description of Change: Clarified language explaining timing of study procedures (vital signs, physical examination, peak flow or spirometry, and clinical assessment using oral food challenge Symptom Scoring Assessment Tool) during BPCFC.

Purpose for Change: To provide clarity regarding timing for assessments (vital signs, physical examination, peak flow or spirometry, and clinical assessment) during BPCFC.

## 20. Section 7.4 (Efficacy)

- a. Description of Change: Added exploratory efficacy endpoints to assess on Day 45.  
Purpose for Change: To reflect the changes in the study design (to reflect addition of BPCFC on Day 45).
- b. Description of Change: Updated text regarding primary and secondary efficacy endpoints.  
Purpose for Change: To differentiate primary and secondary efficacy endpoints from the new exploratory efficacy endpoints.

## 21. Section 9.5 (Efficacy analysis)

- a. Description of Change: Updated statistical analysis methods for primary and secondary endpoints analysis and added statistical analysis methods for new exploratory endpoints.  
Purpose for Change: To reflect the appropriate statistical analysis methods for endpoints based on the changes in the study design.
- b. Description of Change: Added exploratory efficacy endpoints and clarified primary and secondary endpoints.  
Purpose for Change: To reflect the changes in the study design.

## 22. Section 18 (Appendix 2)

- a. Description of change: Added sample collection time points for Day 45 blood tests.  
Purpose for Change: To provide instruction for collecting the Day 45 blood samples prior to the BPCFC.
- b. Description of Change: Added footnote 'd' to reflect the window period for blood sample collection for ex vivo peanut challenge assay.  
Purpose for Change: Added to reflect the extended window period for blood sample collection for ex vivo peanut challenge assay either at screening or on Day 1.

## 23. Administrative Change

Description of Change: Updated Contract Research Organization (CRO) name from Quintiles to QuintilesIMS.

Purpose for Change: To reflect the updated CRO name.

**Protocol ANB020-003: Amendment 1, 01 DEC 2016**

**Replaces: Original: 27 SEP 2016**

1. Protocol Cover Page

Description of Change: Removal of “EnduraCT No.: 2016 002539 14”

Purpose of change: Information not necessary for U.S. only protocol.

2. Section 4.1; Table 4.1 (Schedule of Events)

Description of Change: Added FSH at screening visit and additional footnote to indicate the criteria for testing FSH and collection visit.

Purpose for Change: To include FSH in the screening safety laboratory assessment which was missing in the original protocol.

3. Section 6.2.1

Description of change:

- a. Updated the total blood volume and modified the text to be “The total blood volume for each patient will be approximately 177 mL.”
- b. Revised Table 6.1 (Blood Volume Sampling During Each Visit) to include the updated blood volume required on each study assessment day/visit.

Purpose of change: To reflect the changes in the safety laboratory assessment and to reflect the changes in the amount of blood volume required for laboratory tests.

4. Section 7.1.2; Table 7.1 (Clinical Laboratory Parameters)

Description of change: Added Immunoglobulins (IgA, IgG, IgM, IgE, and IgD) under hematology panel.

Purpose for Change: To include immunoglobulins in the safety laboratory assessments which were missing in the original protocol.

5. Section 7.2

Description of change: Updated the amount of blood volume required for pharmacodynamic test.

Purpose for Change: To reflect the changes in the in the amount of blood required for pharmacodynamic laboratory test.

Figure 1: Schematic of Study Design 13

Document: \\ieedc-nas01a\biosdata\AnaptysBio\ANB020\CYA74393\Biostatistics\Documentation\SAP\Final2018-02-07
Author: [REDACTED] Version Number: Final 1.0
Version Date: 07Feb2018

Template No: CS_TP_BS016 Revision 4
Effective Date: 01Apr2016

Reference: CS_WI_BS005

STATISTICAL ANALYSIS PLAN

AnaptysBio Inc
PROTOCOL ANB020-003
Page 8 of 36

List of Abbreviations and Definitions of Terms

Abbreviation	Definition
AE	Adverse event
ANCOVA	Analysis of covariance
%AUC _{ex}	Percentage of AUC _(0-inf) obtained by extrapolation
AUC _(0-inf)	Area under the concentration-time curve from time zero (predose) extrapolated to infinite time
AUC _(0-last)	Area under the concentration-time curve from time zero (predose) to time of last quantifiable concentration
BLQ	Below the lower limit of quantitation
BMI	Body mass index
BP	Blood pressure
BPCFC	Blind placebo-controlled food challenge
CI	Confidence interval
CL	Systemic clearance following intravenous dosing
C _{max}	Maximum observed concentration
CV	Coefficient of variation
ECG	Electrocardiogram
eCRF	Electronic case report form

Document: \\ieedc-nas01a\biosdata\AnaptysBio\ANB020\CYA74393\Biostatistics\Documentation\SAP\Final2018-02-07
Author: [REDACTED] Version Number: Final 1.0
Version Date: 07Feb2018

Template No: CS_TP_BS016 Revision 4
Effective Date: 01Apr2016

Reference: CS_WI_BS005

STATISTICAL ANALYSIS PLAN

AnaptysBio Inc
PROTOCOL ANB020-003
Page 9 of 36

EOS	End of Study
ET	Early Termination
gCV	Geometric coefficient of variation
Gmean	Geometric mean
HR	Heart rate
ICH	International Council for Harmonisation
IP	Investigational product
IV	Intravenous(ly)
λ_z	Apparent terminal rate constant
LLOQ	Lower limit of quantitation
LS	Least-squares
MedDRA	Medical Dictionary for Regulatory Activities
n	Sample size or number of observations
OFC	Oral Food Challenge
PD	Pharmacodynamic(s)
PK	Pharmacokinetic(s)
R _{sq}	Coefficient of determination
SAE	Serious adverse event

Document: \\ieedc-nas01a\biosdata\AnaptysBio\ANB020\CYA74393\Biostatistics\Documentation\SAP\Final2018-02-07
Author: [REDACTED] Version Number: Final 1.0
Version Date: 07Feb2018

Template No: CS_TP_BS016 Revision 4
Effective Date: 01Apr2016

Reference: CS_WI_BS005

STATISTICAL ANALYSIS PLAN

AnaptysBio Inc
PROTOCOL ANB020-003
Page 10 of 36

SAP	Statistical analysis plan
SAS	Statistical analysis system
SD	Standard deviation
SI	System International
TEAE	Treatment emergent adverse event
$t_{1/2}$	Apparent terminal half-life
t_{max}	Time to maximum observed concentration
V_{ss}	Volume of distribution at steady state following intravenous dosing
V_z	Volume of distribution
WBC	White blood cell
WHO DD	World Health Organization Drug Dictionary

Document: \\ieedc-nas01a\biosdata\AnaptysBio\ANB020\CYA74393\Biostatistics\Documentation\SAP\Final2018-02-07
Author: [REDACTED] Version Number: Final 1.0
Version Date: 07Feb2018

Template No: CS_TP_BS016 Revision 4
Effective Date: 01Apr2016

Reference: CS_WI_BS005

STATISTICAL ANALYSIS PLAN

AnaptysBio Inc
PROTOCOL ANB020-003
Page 11 of 36

1. INTRODUCTION

This document describes the statistical analyses to be performed and data presentations to be produced for this phase II, randomized, double-blind, placebo-controlled, study to evaluate the safety, tolerability and efficacy of single IV infusion of 300 mg ANB020 in 20 Adult Patients with Peanut Allergy.

The purpose of this statistical analysis plan (SAP) is to ensure the credibility of the study findings by specifying the statistical approaches to the analysis of the double-blind data prior to database lock. This SAP was developed based on the International Conference on Harmonization (ICH) E3 and E9 Guidelines and in reference to the following document:

Protocol AnaptysBio ANB020-003 amendment 3 dated 30Jun2017.

Any deviations during the analysis and reporting process from the current SAP will be described and justified in the final report. Analysis issues that suggest changes to the principal features stated in the protocol will be documented in a protocol amendment. Otherwise, the SAP will be updated through an amendment with the changes in the analysis documented in the amendment.

2. STUDY OBJECTIVES

2.1. PRIMARY OBJECTIVES

To assess the safety and tolerability of single dose administration of ANB020 in adult patients with peanut allergy

To measure the response of adult patients with peanut allergy on Day 14 following an oral blind placebo-controlled food challenge (BPCFC) threshold and total cumulative peanut dose tolerated after administration of ANB020 or placebo compared to cumulative baseline peanut BPCFC

2.2. SECONDARY OBJECTIVES

To compare the symptoms to peanut antigen challenge on Day 14 using the Oral Food Challenge (OFC) Symptoms Scoring Assessment Tool after administration of ANB020 or placebo compared to baseline peanut BPCFC symptoms

To describe the limited pharmacokinetics (PK) of ANB020 following a single, intravenous (IV) dose

Document: \\ieedc-nas01a\biosdata\AnaptysBio\ANB020\CYA74393\Biostatistics\Documentation\SAP\Final2018-02-07
Author: [REDACTED] Version Number: Final 1.0
Version Date: 07Feb2018

Template No: CS_TP_BS016 Revision 4
Effective Date: 01Apr2016

Reference: CS_WI_BS005

STATISTICAL ANALYSIS PLAN

AnaptysBio Inc
PROTOCOL ANB020-003
Page 12 of 36

2.3. EXPLORATORY OBJECTIVES

- To assess the effect of ANB020 on circulating serum cytokines
- To assess the effect of ANB020 on leukocytes within whole blood
- To compare the immune response of ANB020 to placebo dosed patients in the ex vivo peanut antigen challenge
- To measure the response of adult patients with peanut allergy on Day 45 following an oral BPCFC threshold and cumulative peanut dose tolerated after administration of ANB020 or placebo compared to cumulative baseline peanut BPCFC
- To compare the symptoms to peanut antigen challenge on Day 45 using the OFC Symptoms Scoring Assessment Tool after administration of ANB020 or placebo compared to baseline peanut BPCFC symptoms

3. STUDY DESIGN

3.1. GENERAL DESCRIPTION

This is a Phase II, double-blind, placebo-controlled, proof of concept study to assess the safety and tolerability of ANB020 in adult patients with peanut allergy. This study will also investigate the effects of ANB020 or placebo in adult peanut allergic patients following an oral BPCFC at 2 and 6 weeks post ANB020 or placebo administration. The effects of ANB020 on the immune response to peanut upon ex vivo peanut antigen challenge will be evaluated.

No formal statistical calculation has been performed for sample size. Approximately 20 patients will be enrolled in the study.

Patients will be randomized in a 3:1 ratio to receive ANB020 (300 mg/100 mL) or matching 100 mL placebo (0.9% sodium chloride) administered through intravenous route.

A schematic of the study design is included as [Figure 1](#):

Document: \\ieedc-nas01a\biosdata\AnaptysBio\ANB020\CYA74393\Biostatistics\Documentation\SAP\Final2018-02-07
Author: [REDACTED] Version Number: Final 1.0
Version Date: 07Feb2018

Template No: CS_TP_BS016 Revision 4
Effective Date: 01Apr2016

[figure not shown]
Reference: CS_WI_BS005

STATISTICAL ANALYSIS PLAN

AnaptysBio Inc
PROTOCOL ANB020-003
Page 13 of 36

Figure 1: Schematic of Study Design

3.2. SCHEDULE OF EVENTS

The schedule of events can be found in Section 4.1, [Table 4.1](#) of the protocol

Document: \\ieedc-nas01a\biosdata\AnaptysBio\ANB020\CYA74393\Biostatistics\Documentation\SAP\Final2018-02-07
Author: [REDACTED] Version Number: Final 1.0
Version Date: 07Feb2018

Template No: CS_TP_BS016 Revision 4
Effective Date: 01Apr2016

Reference: CS_WI_BS005

STATISTICAL ANALYSIS PLAN

AnaptysBio Inc
PROTOCOL ANB020-003
Page 14 of 36

3.3. CHANGES TO ANALYSIS FROM PROTOCOL

No changes from the analysis planned in the protocol were made.

4. PLANNED ANALYSIS

This SAP describes the methodology for final analysis.

4.1. DATA MONITORING COMMITTEE (DMC)

No DMC is planned of this study.

4.2. INTERIM ANALYSIS

No interim analysis is planned for this study.

4.3. FINAL ANALYSIS

All final, planned statistical analyses identified in this SAP will be performed by the IQVIA Biostatistics department.

Analysis of the PK and pharmacodynamics (PD) of ANB020 and the associated figures, will be the responsibility of the clinical pharmacokineticist (PK analyst) at IQVIA. The PK/PD summaries and data listings will be the responsibility of the ECD biostatistician at IQVIA.

5. ANALYSIS SETS

Summaries will be presented by treatment and overall as appropriate.

Listings will be presented for all patients available in the data transfer received from data management.

The following analysis sets will be used:

5.1. ALL PATIENTS SCREENED [SCR]

Patients who have signed the informed consent form and have been screened.

5.2. RANDOMIZED ANALYSIS SET [RND]

All patients who have been allocated to a randomized treatment arm, regardless of whether they received the planned treatment or not. Patients will be considered according to their randomized

Document: \\ieedc-nas01a\biosdata\AnaptysBio\ANB020\CYA74393\Biostatistics\Documentation\SAP\Final2018-02-07
Author: [REDACTED] Version Number: Final 1.0
Version Date: 07Feb2018

STATISTICAL ANALYSIS PLAN

AnaptysBio Inc
PROTOCOL ANB020-003
Page 15 of 36

treatment.

5.3. FULL ANALYSIS SET [FAS]

All patients who have received ANB020 or placebo and were present in the study until Day 14 with post baseline BPCFC and OFC results present. The full analysis set will be used for all efficacy analyses. Patients will be considered according to their randomized treatment.

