- l If any objective reaction occurred at Day 14/15, the BPCFC (peanut and placebo oral food challenge) will not be required but may be performed at the discretion of the Investigator
- m The FSH levels will be obtained only on postmenopausal patients defined as aged over 45 years with at least 1 year of amenorrhea. Blood samples to determine the FSH levels will be obtained only at screening.
- n If the Investigator decides to complete the oral food challenge over two days, please refer to Day 46 and appropriate footnotes for guidance.
- o If the BPCFC is continued on Day 46, all assessments related to the BPCFC will be performed on Day 46. Concomitant medications and adverse events will also be recorded on Day 46. All laboratory/diagnostic tests scheduled for the EOS visit will be performed on day 45.
- P If the patient's ET visit is between Day 35 to 45, and the termination is for non-medical reasons, the BPCFC will be administered during the ET visit. If the ET visit is before Day 35, the BPCFC will not be repeated.
- q Informed consent must be obtained prior to participation in the study.

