#### **4.3.5 Patient Withdrawal**

All patients are free to withdraw from participation in the study at any time, for any reason, specified or unspecified, and without prejudice to further treatment. The inclusion and exclusion criteria are to be followed explicitly. If a patient who does not meet the criteria is inadvertently enrolled, that patient should be withdrawn from the study. AnaptysBio and QuintilesIMS must be contacted, and if the patient has received ANB020 or placebo, the patient must be followed up until EOS (Day 45) for any AEs and/or SAEs.

In addition, the patients will be withdrawn from the study under the following circumstances:

- Prior to IP administration, the Investigator decides that the patient should be withdrawn or is at risk. If this decision is made because of an AE or a clinically significant laboratory value, the IP should not be administered and appropriate measures are to be taken. AnaptysBio and/or QuintilesIMS is to be notified immediately.
- The patient is unwilling to continue in the study.
- Lack of compliance with protocol.
- The Investigator or AnaptysBio, for any reason, stops the study.
- If a female patient becomes pregnant.
- New information suggests taking part in the study may not be in the participant's best interest.

Patients who discontinue the study early will have early termination (ET) procedures performed as shown in [Table 4.1](#). Patients who are randomized and dosed with ANB020 or placebo and discontinued from the study after Day 14 will not be replaced. All patients who discontinue the study prior to completing the Day 14 study assessments will be replaced.

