##### Full Analysis Set

All patients who have received ANB020 or placebo and present in study till Day 14. The full analysis set will be used for all efficacy analyses.

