7.3. MISSING DATA

No imputations will be performed on missing data.

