17.1.2. ANALYSIS OF PRIMARY EFFICACY ENDPOINT

The null hypothesis for the primary efficacy analysis is:

H0: There is no difference in change from baseline on day 14 for total cumulative tolerated peanut dose during BPCFC between ANB020 and placebo.

Document: \\ieedc-nas01a\biosdata\AnaptysBio\ANB020\CYA74393\Biostatistics\Documentation\SAP\Final2018-02-07
Author: [REDACTED] Version Number: Final 1.0
Version Date: 07Feb2018

STATISTICAL ANALYSIS PLAN

AnaptysBio Inc
PROTOCOL ANB020-003
Page 23 of 36

Vs the alternative:

H1: There is a difference in change from baseline on day 14 for total cumulative tolerated peanut dose during BPCFC between ANB020 and placebo

The primary efficacy analysis will be carried out for the FAS population.

The actual and change from baseline values of primary efficacy endpoints will be summarized using appropriate descriptive statistics by treatment at all time points where assessment is done. Change from baseline will be evaluated where possible.

Regarding the primary efficacy endpoint, change from baseline on day 14 of tolerated dose will be compared between ANB020 and placebo using an ANCOVA with treatment as fixed effect and baseline results as a covariate.

The following statistics will be presented:

- o Treatment difference
- o Standard error of treatment difference
- o 95% CI
- o p-value

The treatment difference and 95% CI will also be presented graphically.

Patient-wise data listings will be provided.

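### SAP 5.3 narrows the protocol's full analysis set without declaring it, and the completers-only primary comparison has no planned check

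*SAP*

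**What the plan says.** Protocol 9.1.1 defines the FAS as "All patients who have received ANB020 or placebo and present in study till Day 14". SAP 5.3 keeps dosing and presence to Day 14 but requires in addition that patients "were present in the study until Day 14 with post baseline BPCFC and OFC results present". SAP 3.3 then states: "No changes from the analysis planned in the protocol were made".

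SAP 17.1.2 ties the primary result to this set: "The primary efficacy analysis will be carried out for the FAS population". The change in tolerated dose at Day 14 is "compared between ANB020 and placebo using an ANCOVA with treatment as fixed effect and baseline results as a covariate".

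Three further rules decide who can contribute:

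- **Replacement** (protocol 4.3.5): "All patients who discontinue the study prior to completing the Day 14 study assessments will be replaced".
- **Early termination** (footnote to protocol Table 4.1): "If the ET visit is before Day 35, the BPCFC will not be repeated".
- **Missing data** (SAP 7.3): "No imputations will be performed on missing data". Protocol 9.4.3 has the same rule, placed under the safety analyses.

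**The concern.** There are two separate problems.

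The first is an undeclared difference between the documents. Protocol 9.0 says that changes to the analysis methods are to be documented in the SAP, and the SAP reports none. Version drift does not appear to explain the gap. The SAP cites Amendment 3, and the protocol's summaries of changes for Amendments 4 and 5 list nothing for section 9.1.1. The added condition also works against the primary endpoint, because it makes a tolerated-dose analysis depend on a symptom score.

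The second is that membership of the only efficacy set depends on what happens after randomisation and dosing. If the reasons for leaving differ by arm, the ANB020–placebo difference describes those who reached Day 14 rather than those who were treated. Replacement refills the count but does not restore the randomised comparison. A Randomized Analysis Set is defined, but no efficacy analysis uses it, and neither document plans a sensitivity analysis for missing Day 14 doses.

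**Working it through.** The plan states no power or precision figure to reproduce, since protocol 9.1 says the sample size is not based on power. The check compares the definitions first and then sets a scale.

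**1. Whom does the SAP's extra condition remove from the primary analysis?**

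| Dosed patient | Protocol FAS | SAP FAS | Contributes a Day 14 change? |
|---|---|---|---|
| Left before Day 14 | out | out | no |
| Present, no Day 14 dose recorded | in | out, unless Day 45 results count | no, under either definition |
| Present, Day 14 dose, no post-baseline OFC score | in | **out** | **yes under the protocol, no under the SAP** |
| Present, both results | in | in | yes |

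Only the third row changes the primary ANCOVA. The same patient is also lost from the tolerated-dose summaries and the Day 45 repeated-measures model. Such a patient has not discontinued, so the replacement rule does not apply.

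**2. What would one such loss cost?** Inputs: 15 ANB020 and 5 placebo (protocol 6.2.2). Ignoring chance baseline imbalance, the standard error of the difference is the residual SD times sqrt(1/n_A + 1/n_P).

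- 15:5 gives sqrt(1/15 + 1/5) = 0.516.
- 15:4 gives sqrt(1/15 + 1/4) = 0.563, a ratio of 1.090 (+9.0%).
- 14:5 gives sqrt(1/14 + 1/5) = 0.521, a ratio of 1.009 (+0.9%).

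With n − 3 degrees of freedom (intercept, treatment, baseline), the 95% CI half-width goes from 1.09 residual SD at 15:5 (17 df) to 1.19 at 15:4 (16 df).

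**3. How much can the completers-only restriction hide?** The documents give no dropout rate, so d, the number of dosed patients who leave early and are replaced, is an assumption. If 20 patients are analysed, 20 + d are dosed, and the share outside the analysis is d/(20 + d). That is 1/21 = 4.8% for d = 1, rising to 5/25 = 20.0% for d = 5.

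The tolerated dose lies between 0 and 500 mg, because the challenge steps in protocol 6.1.1 sum to 5 + 20 + 50 + 100 + 100 + 100 + 125 = 500. With n patients observed and d unseen in an arm, the mean over all n + d is undetermined over a width of 500·d/(n + d):

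- one unseen placebo patient: 500/6 = 83.3 mg;
- one unseen ANB020 patient: 500/16 = 31.2 mg;
- one in each arm: 114.6 mg for the treatment difference.

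These are worst-case widths, not estimates of bias.

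**The case against.** The strongest reply is that little depends on the SAP wording. A reader might infer that SAP 5.3 creates the completers-only analysis, but it does not. The protocol's FAS already requires presence to Day 14, early leavers have no post-baseline challenge, and nothing is imputed, so the same early leavers would be missing under the protocol's definition. The residual case is also unlikely. The symptom tool is scored on site at five time points around each challenge (protocol 6.1.1). SAP 5.3 names neither a time point nor a visit, so read literally any one post-baseline score, even at Day 45, would do. All of this stands. It limits the size of the first problem, and it also shows that the condition is undefined.

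A reader might also infer an upward bias. If k ANB020 patients left with no gain and were replaced in the same arm, the completers' ANB020 mean would exceed the all-dosed mean by k/15, or 7%, 13% and 20% for k = 1, 2 and 3. The documents do not support using this as an estimate. It concerns one arm mean rather than the treatment difference. It places every dropout on ANB020 with zero gain, and neither document says how replacements are allocated to an arm.

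Nor does protocol 4.3.5 list adverse events after dosing as a reason for withdrawal, because its adverse-event clause applies before the infusion. The disposition table shell does allow for discontinuation due to an adverse event. A dosed patient later found ineligible is still followed to Day 45 for safety.

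Finally, the study is unpowered and described as exploratory, all dosed patients count in the safety analysis, and the disposition table will show how many patients are in the FAS by arm. Visible counts do not show whether the result is sensitive to those missing, and SAP 17.1.2 still reports a p-value and a 95% CI.

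**Conclusion.** The concern holds in two limited parts.

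- **Undeclared narrowing.** SAP 5.3 is stricter than protocol 9.1.1, and SAP 3.3 is wrong to report no change. The effect on the primary analysis is confined to patients with a Day 14 dose and no post-baseline symptom score. This is uncommon, but one such placebo patient would cost 9% in standard error.
- **Unchecked completers-only comparison.** This comes mainly from the protocol. Its possible influence could be large relative to the 500 mg scale because the placebo arm has only 5 patients, but the size and direction are unknown.

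The figures assume the planned 15:5 split and illustrative exclusions. If no one leaves before Day 14 and no result is missing, the two definitions select the same patients and neither problem affects the results.

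**What to change.** Before database lock:

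1. In SAP 5.3, delete the joint requirement for challenge and symptom results. State that each endpoint uses all FAS patients who have that endpoint at the named visit, Day 14 for the primary.
2. Reconcile the definition with protocol 9.1.1 and list any remaining difference in SAP 3.3.
3. Keep the observed-data ANCOVA as primary. Making zero change the primary rule for early leavers would be a debatable single-value imputation that contradicts the documents' missing-data rules.
4. Add one pre-specified sensitivity analysis on all randomised and dosed patients, originals and replacements. State how a missing Day 14 dose is handled for every withdrawal reason, for example change = 0 together with a range or the bounds shown above. Note this analysis as an exception in SAP 7.3.

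The cost is SAP wording and one extra analysis, with no new data. The added result may look less favourable if early withdrawals occur.
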